### 3.4 Schedule of Events

Visit Day	Screening (Day -7 + 1)	Day 0	Day 7	Day 14	Day 28	Day 35
Informed Consent / Assent	X					
Medical History	X					
Physical Exam		X				X
Inclusion/Exclusion Criteria	X	X				
IRT	X	X				X
Vital Signs	X	X	X	X	X	X
Weight	X	X				
Height	X					
Temperature		X	X			
Hematology, Chemistry and Iron Indices 	X	X	X	X	X	X
Serum Pregnancy Test	X					X
Concomitant Medications	X	X	X	X	X	X
IBD Treatment / ESA Stability (if applicable)	X	X	X	X	X	X
Adverse Event Assessments		X	X	X	X	X
Randomization		X				
Injectafer ® Dosing		X	X			
Pharmacokinetic Sampling 		X	X			
Oral Iron Dosing		X	X	X	X	
Oral Iron Dispensing		X	X	X		
Oral Iron Compliance Assessment			X	X	X	

For a full description of central laboratory assessments, refer to Protocol Section 6.4.

Blood samples for pharmacokinetic analysis will be collected pre-dose, immediately (within 5 minutes) post-dose, and 60 minutes post-dose for participants receiving FCM. For a full description of the pharmacokinetic parameters, refer to Protocol section 6.3.6.

## 4.0 PARTICIPANT SELECTION

### 4.1 Number and Type of Participants

Approximately 72 participants who have given written informed consent/assent with a diagnosis of IDA who fulfill the inclusion criteria and do not meet any of the exclusion criteria will be randomized to receive either FCM or Oral Iron.

### 4.2 Screening Phase

A subject who enters the screening phase will be assigned, via the IRT system, a unique screening number. From the time of consent until the start of treatment with study drug, the participant will not receive any form of supplemental iron outside of the study (intravenous or blood transfusion iron from 4 weeks prior to consent or oral iron including multivitamins with iron from time of consent). Dietary iron intake will not be restricted during participation in the study.

If the participant does not qualify for study entry, the participant should be entered into the IRT system as a screen failure. Participants can be re-screened once (**See section 6.2**).

#### 4.2.1 Inclusion Criteria

1. Male or female participants 1 to 17 years of age with assent to participation and his/her parent or guardian is willing and able to sign the informed consent approved by the Independent Review Board / Ethics Committee.
2. Screening hemoglobin <11 g/dL.
3. Screening ferritin  $\leq$  300 ng/mL and TSAT <30%.
4. Documented history of an inadequate response to any oral iron therapy for at least 8 weeks (56 days) prior to randomization.
5. If receiving an ESA: stable ESA therapy (+/- 20% of current dose) for at least 8 weeks prior to the qualifying screening visit and no ESA dosing or product changes anticipated for the length of the trial.
6. If undergoing treatment for IBD must be on stable therapy for at least 8 weeks prior to consent.

#### 4.2.2 Exclusion Criteria

1. Known history of hypersensitivity reaction to any component of FCM.
2. Previous randomization and treatment in this study or any other clinical study of FCM.
3. History of acquired iron overload, hemochromatosis, or other iron accumulation disorders.
4. Significant severe diseases of the liver, hematopoietic system, cardiovascular system, psychiatric disorder, or other conditions which on the opinion of the investigator may place a subject at added risk.
5. Any existing non-viral infection.
6. Known history of positive hepatitis B antigen (HBsAg) or hepatitis C viral antibody (HCV) with evidence of active hepatitis.

7. Known history of positive HIV-1/HIV-2 antibodies (anti-HIV).
8. Anemia due to reasons other than iron deficiency (e.g., hemoglobinopathy and vitamin B12 or folic acid deficiency) that have not been corrected.
9. Intravenous iron and /or blood transfusion in the 4 weeks prior to consent.
10. Administration and / or use of an investigational product (drug or device) within 30 days of screening.
11. Alcohol or drug abuse within the past six months.
12. Female participant who is pregnant or lactating, or sexually active female of childbearing potential not willing to use an acceptable form of contraceptive precautions during the study.
13. Unable to comply with study procedures and assessments.

### **4.3 Participant Assignment and Randomization Process**

Participants who satisfy the inclusion requirements and no exclusionary criteria will be eligible to participate in this study and entered into the IRT system. Randomization will occur in a 1:1 ratio to either Group A, participants receiving FCM, or Group B, participants receiving oral iron (oral solution drops, elixir or oral tablets). Randomization will be stratified by baseline hemoglobin (<10, ≥10 g/dL) and age (1 to <12 and ≥12 to 17 years).

The oral ferrous sulfate formulation received will be based on the participant's age, such that: infants and children (1 to <4 years of age) will receive ferrous sulfate drops, children (≥4 to <12 years of age) will receive ferrous sulfate elixir or ferrous sulfate tablets, and adolescents (≥12 to 17 years of age) will receive ferrous sulfate tablets. Participants who experience adverse clinical symptoms due to the oral iron during the treatment phase may have their weight-based dose of ferrous sulfate reduced from 6 mg/kg to 3 mg/kg. If the participant is receiving tablets, the dose will be reduced from one tablet taken twice daily to one tablet per day.

### **4.4 Withdrawal from Study**

Any participant who wishes to withdraw from the study may do so at any time without the need to justify their decision. The investigator may withdraw a participant from active study treatment at any time if it is felt to be in the best interest of the participant.

### **4.5 Discontinuation from Study Drug**

Participants may elect to discontinue study drug, but wish to remain in the study for follow-up. In those situations, patients will be asked to continue the normal clinical trial schedule for ascertainment of safety events.

### **4.6 Concomitant Intervention**

Concomitant intervention is defined as follows:

- Blood transfusion.
- Use of IV or oral iron outside of protocol.
- Increase in erythropoietin for any reason (Day 0 thru Day 35).

- Change in IBD treatment

When concomitant intervention occurs, the date of the intervening event should be recorded in the source documents, and the electronic Case Report Form (eCRF). The participant should continue in the study as scheduled.

## 5.0 STUDY DRUG

### 5.1 Formulation, Packaging and Storage

All investigational medication to be used in this study [supplied by American Regent, Inc.] will have been prepared according to Good Manufacturing Practices (GMP).

FCM (trade name, Injectafer®) will be supplied as 15 ml vials, containing 750 mg of iron as 5% w/v iron containing a polynuclear iron(III)-hydroxide 4(R)-(poly-(1→4)-O α -D-glucopyranosyl)-oxy-2 (R), 3(S), 5(R), 6-tetrahydroxy-hexonate complex in a solution of water for injection [50 mg/ml] and will be labeled according to FDA investigational regulatory requirements.

Oral iron will be provided depending on participant's age as either blister packs of oral iron tablets or oral liquid formulation (drops or elixir) in pre-filled syringes.

All study drugs (FCM and ferrous sulfate) must be kept in a secure place at the investigational site, and stored at room temperature (See USP). The study medication should not be frozen. Vials of FCM may not be used for more than 1 dose, or for more than 1 participant. All FCM vials, oral iron blister packs and syringes (used and unused) should be kept by the study staff for reconciliation by the monitor. Following reconciliation, sites may destroy used and unused study drug on site using local procedures, provided a drug destruction policy is in place, or it may be returned to American Regent, Inc.

### 5.2 Drug Administration/Regimen

The Principal Investigator or designee will supervise administration of the study drug to participants. Group B (Ferrous sulfate) the first dose of will be administered before the end of the Day 0 visit.

**Group A:** Group A (FCM) will receive a dose of FCM at 15 mg/kg to a maximum single dose of 750 mg (whichever is smaller) on Days 0 and 7 for a maximum total dose of 1500 mg. FCM will be administered as either an undiluted IV push at a rate of 100 mgs (2 mL)/minute OR in no more than 250 mL of normal saline and infused over 15 minutes.

**Group B:** Group B (Oral Ferrous sulfate) will receive an age-dependent formulation of oral ferrous sulfate daily for 28 days as follows: participants <12 years of age will receive 6 mg (elemental iron)/kg/day divided into 2 daily doses of an oral liquid formulation, either drops or elixir, and participants ≥12 will receive 2 daily doses of oral tablets. Infants and children (ages 1 to <4 years) will receive oral ferrous sulfate drops, while children (ages ≥4 to <12 years)

will have the option to receive oral ferrous sulfate elixir or oral ferrous sulfate tablets. Adolescents (ages  $\geq 12$  to 17 years) will receive an oral ferrous sulfate tablet (65 mg of elemental iron/tablet/dose) twice a day (BID). The maximum daily dose for all participants is 130 mg of elemental iron.

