### **Study Drug**

#### **Administration**

**Group A (FCM)** will receive 2 doses (Day 0 and Day 7) of FCM at 15 mg/kg to a maximum single dose of 750 mg (whichever is smaller) up to a maximum total dose of 1500 mg. FCM will be administered as either an undiluted IV push at a rate of 100 mg (2 mL)/minute OR in no more than 250 mL of normal saline and infused over 15 minutes.

**Group B (Oral ferrous sulfate)** will receive an age-dependent formulation of oral ferrous sulfate daily for 28 days as follows: participants <12 years of age will receive 6 mg (elemental iron)/kg/day divided into 2 daily doses of an oral liquid formulation, either drops or elixir, and participants  $\geq 12$  will receive 2 daily doses of oral tablets. Infants and children (ages 1 to <4 years) will receive oral ferrous sulfate drops, while children (ages  $\geq 4$  to <12 years) will have the option to receive oral ferrous sulfate elixir or oral ferrous sulfate tablets. Adolescents (ages  $\geq 12$  to 17 years) will receive an oral ferrous sulfate tablet (65 mg of elemental iron/tablet/dose) twice a day (BID). The maximum daily dose for all participants is 130 mg of elemental iron.

**Patient  
Assessments**

All participants who provide informed consent/assent, meet inclusion criteria, and do not meet exclusion criteria will be randomized. Starting on Day 0 (the time of study drug dosing) through Day 35, all randomized participants will be subject to safety assessments including vital signs (including sitting heart rate and blood pressure), laboratory samples include hematology, chemistries and iron indices, and adverse event queries. Participants receiving oral iron treatment will be assessed for degree of compliance.

**Primary  
Endpoint:**

Change in hemoglobin from baseline to Day 35.

**Secondary  
Endpoints:**

Change in ferritin from baseline to Day 35  
Change in TSAT from baseline to Day 35  
Changes from baseline in hemoglobin, ferritin, TSAT, and reticulocyte hemoglobin content throughout the study.  
Pharmacokinetic assessments, including  $C_{max}$ ,  $T_{max}$ ,  $AUC_{0-time\ last}$  measured concentration,  $AUC_{0-infinity}$ ,  $T_{1/2}$ , MRT, Cl,  $V_D$ ,  $V_{Dc}$ ,  $V_{Dss}$ , and  $V_{Darea}$ .

**Study duration  
per participant:**

Approximately 6 weeks

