### **3.2 Rationale of Study Design and Choice of Control Groups**

Oral ferrous sulfate was selected as the active comparator because in addition to tablets, liquid formulations suitable for administration to pediatric participants in different age

groups are available. This iron salt is the most widely prescribed oral iron preparation for use in the treatment of pediatric IDA, relative to other preparations, according to a survey of pediatric hematology/oncology specialists. Ferrous sulfate drops, (15 mg elemental iron/mL), may be used as an iron supplement for infants and children up to 4 years of age, per manufacturer labeling. Oral ferrous sulfate elixir will be provided as an alternative preparation to oral tablets in order to ameliorate the difficulty of swallowing tablets with children. Per the recommended total daily dose of oral elemental iron for the treatment of IDA in pediatric patients ranges between 3-6 mg/kg/day divided into one to three doses, a total daily dose of 6 mg/kg/day divided into 2 doses (maximum daily dose of 130 mg of elemental iron) was selected for all ages based on the most common practice of pediatric hematology physicians in the United States. Additionally, the simplified regimen may minimize adverse effects associated with high-dose oral iron therapy and thus improve medication adherence.

With respect to FCM, doses of 15 mg/kg with a maximum of 750 mg per dose have been selected based off evidence generated from American Regent’s Phase II dose-finding PK/PD study in which cohorts received single, weight-based doses of FCM at either 7.5 mg/kg or 15 mg/kg. Results from this study demonstrate that the higher weight-based dose is both efficacious and safe. The mean increase from baseline to Day 35 was larger for participants in Cohort 2 receiving 15 mg/kg ( $2.8 \pm 1.15$  g/dL) than those in Cohort 1 receiving 7.5 mg/kg ( $1.9 \pm 1.38$  g/dL). The mean increase in ferritin and TSAT at Day 35 was  $35.1 \pm 98.22$  ng/mL and  $9.9 \pm 11.54\%$ , respectively, for Cohort 1 (N=16) and  $52.4 \pm 31.7$  ng/mL and  $13.5 \pm 6.88\%$ , respectively, for Cohort 2 (N=18), respectively. (Table 1)

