### 6.3 Treatment Phase (Day 0 to Day 35)

#### 6.3.1 Day 0 Visit

The following will be obtained and/or completed before contacting IRT for randomization:

For all participants:

- Verify all inclusion and exclusion criteria (See section 4.2.1 and 4.2.2)
- Physical exam
- Review concomitant medications (to include ESA and IBD stability, if applicable).

A participant who develops a bacterial infection during the screening phase should be discontinued and treated appropriately. These participants may be re-screened, one time, once the enrolling physician deems the participant would qualify for study entry. The participant will need to re-sign a new consent / assent form and all screening procedures in section 6.2 will need to be repeated.

After verifying the eligibility of the participant, the IRT system will then be contacted by a study team member. Randomization will be stratified by hemoglobin (<10, ≥10 g/dL) and age (1 to <12 and ≥12 to 17 years), and randomized in a 1:1 ratio to either Group A (FCM at 15 mg/kg to a maximum single dose of 750 mg on Days 0 and 7 for a maximum total dose of 1500 mg) or Group B (Ferrous sulfate, dose and regimen dependent upon age and weight, twice daily for 28 days).

After a randomization number has been obtained, the **first dose** of oral ferrous sulfate will be administered in the clinic according to the following: infants and children (1 to <4 years of age) will receive ferrous sulfate drops; children (≥4 to <12 years of age) will receive ferrous sulfate elixir or ferrous sulfate tablets; and adolescents (≥12 to 17 years of age) will receive ferrous sulfate tablets.

A sufficient quantity of doses for a 7-day period will be dispensed to the parent or guardian of the participant. The parent or guardian of the participant will be responsible for the administration of two daily doses of oral ferrous sulfate to the participant.

After assignment of the treatment group, the following will occur:

All participant's (prior to study drug administration/dispensing, if applicable) on Day 0:

- Blood samples for central lab hematology, chemistries, and iron indices (Group

- A participants will have an additional blood sample for PK prior to dosing)
- Vital signs: temperature, sitting heart rate and blood pressure
- Weight

Group A:

- Blood samples for PK immediately (within 5 minutes) post-dose and 60 minutes post dose.
- Verify amount of single FCM dose (15mg/kg up to a maximum single dose of 750 mg).

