### **6.3.5 Oral Iron Dose Reduction during the Treatment Phase**

Participants who experience adverse events possibly or probably due to the oral iron during the treatment phase will have their dose of ferrous sulfate reduced from 6 mg/kg to 3 mg/kg while maintaining the same frequency of twice per day. If the participant is receiving tablets, the dose will be reduced from one tablet taken twice daily to one tablet per day.

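### Children aged 4 to <12 may choose tablets but have no tablet dose; the only stated regimen, 65 mg twice daily, exceeds the protocol's 6 mg/kg/day below 21.7 kg

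*Protocol*

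**What the plan says.** The Group B paragraph of Protocol Section 5.2, and the matching synopsis paragraph, make four statements:

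- Dose under 12 years: "participants <12 years of age will receive 6 mg (elemental iron)/kg/day divided into 2 daily doses of an oral liquid formulation", with drops and elixir named as the liquids.
- Formulation at ages 4 to <12: these children "will have the option to receive oral ferrous sulfate elixir or oral ferrous sulfate tablets". No strength, number of tablets or weight rule follows.
- Ages 12 to 17: one 65 mg tablet twice a day.
- Cap: "The maximum daily dose for all participants is 130 mg of elemental iron".

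Other sections bear on the tablet dose without settling it:

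- Section 3.2 says that "a total daily dose of 6 mg/kg/day divided into 2 doses (maximum daily dose of 130 mg of elemental iron) was selected for all ages", and cites 3 to 6 mg/kg/day as the recommended pediatric range.
- Section 6.3.1 describes Group B treatment as "Ferrous sulfate, dose and regimen dependent upon age and weight, twice daily for 28 days".
- Section 5.1 describes the supply as "either blister packs of oral iron tablets or oral liquid formulation (drops or elixir) in pre-filled syringes", with no tablet strength.
- Section 6.3.5 says: "If the participant is receiving tablets, the dose will be reduced from one tablet taken twice daily to one tablet per day". The synopsis and Sections 3.1 and 4.3 say the same. None of them limits this by age.
- SAP Section 1.3.1 repeats the tablet option without a dose.

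**The concern.** For ages 4 to <12 the two consecutive sentences in Section 5.2 conflict: the dose is tied to a liquid, yet tablets are allowed. A site with a light child who prefers tablets has a mg/kg target but no rule for meeting it with tablets. The only strength and frequency it can find is the adolescent one, and the dose-reduction text points the same way.

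At stake is how much iron the smallest tablet-takers receive. Section 3.2 says the regimen was chosen partly to limit the adverse effects of high-dose oral iron, and safety relative to oral iron is part of the primary objective. Two sites could also dose identical children differently while each believed it was following the protocol.

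The planned summaries would not show an excess directly. SAP Section 5.1 measures oral compliance against the dose prescribed, so a child prescribed and taking 130 mg/day scores 100% at any weight. SAP Section 7.1 summarizes oral dose in mg, not mg/kg.

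**Working it through.** **Inputs**

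- Tablet strength 65 mg, twice daily (Section 5.2, adolescent sentence).
- Selected dose 6 mg/kg/day, maximum 130 mg/day (Section 3.2).
- Cited range 3 to 6 mg/kg/day (Section 3.2).
- Treatment for 28 days (Section 5.2).
- Body weight: the documents give none for this age group. The weights below are assumptions.

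**The plan's own figure.** 2 × 65 = 130 mg/day, which reproduces the stated maximum. The cap is therefore exactly two tablets and cannot restrain a two-tablet regimen.

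**Threshold.** Two tablets a day exceed 6 mg/kg/day when 130/weight > 6, that is, when weight < 130/6 = 21.67 kg.

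**Can whole tablets meet the target?** One a day gives exactly 6 mg/kg/day only at 65/6 = 10.83 kg, and two a day only at 21.67 kg. Between those weights the target needs a fraction of a tablet. At 16 kg it is 6 × 16 = 96 mg/day, or 96/65 = 1.48 tablets. No splitting or rounding rule is given.

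**Dose by assumed weight**

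| Weight (kg) | Target, min(6 × weight, 130) (mg/day) | Two tablets, 130/weight (mg/kg/day) | Above 6 mg/kg/day | One tablet, 65/weight (mg/kg/day) |
|---|---|---|---|---|
| 14 | 84 | 9.29 | 55% | 4.64 |
| 16 | 96 | 8.13 | 35% | 4.06 |
| 18 | 108 | 7.22 | 20% | 3.61 |
| 20 | 120 | 6.50 | 8% | 3.25 |
| 22 | 130 | 5.91 | none | 2.95 |
| 25 | 130 | 5.20 | none | 2.60 |
| 30 | 130 | 4.33 | none | 2.17 |
| 40 | 130 | 3.25 | none | 1.62 |

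**Total over 28 days, two tablets a day against elixir**

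- Two tablets: 130 × 28 = 3,640 mg.
- Elixir at 16 kg: 6 × 16 × 28 = 2,688 mg. Difference 3,640 − 2,688 = 952 mg.
- Elixir at 20 kg: 6 × 20 × 28 = 3,360 mg. Difference 280 mg.
- At or above 21.67 kg the elixir dose is capped at 130 mg/day. Difference 0.

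**The case against.** The best reply is that the controlling dose is already stated. Section 3.2 sets 6 mg/kg/day for all ages without limiting it to a formulation, Section 6.3.1 makes the dose depend on weight, and Section 5.2 repeats 6 mg/kg/day under 12 years. Giving 130 mg/day to a 16 kg child would go against all three. On this view the conflict is leftover drafting: the amendment log shows that Amendment 2 added the tablet option, and the liquid-only sentence stayed. It is true that the protocol does not instruct 130 mg/day for these children. But the mg/kg target cannot be met with whole 65 mg tablets at the affected weights, and the only tablet regimen described is the one that overshoots.

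A second reply is that few children can be affected. A child must be among the roughly 36 randomized to oral iron, be 4 to <12 years old, choose tablets and weigh under 21.7 kg. Section 3.2 says elixir is offered because tablets are hard for children to swallow, so the smallest may seldom choose them. This stands: the number is unknown and could be zero. However, no minimum weight is set for entry or for tablets.

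A third is that adverse events are assessed at every visit and Section 6.3.5 then cuts tablets to one a day, which at 14 to 20 kg falls within the cited 3 to 6 mg/kg/day. That limits exposure, but only after the child has had an adverse event.

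**Conclusion.** The concern holds. Section 5.2 and the synopsis give ages 4 to <12 a liquid-only dose and then a tablet option with no dose. The one tablet regimen available exceeds both the selected 6 mg/kg/day and the top of the cited range below 21.7 kg.

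The textual gap and the threshold follow from the documents alone. The size of the excess, 8% at 20 kg to 55% at 14 kg, rests on assumed weights and on a site adopting the adolescent regimen. No effect on the primary hemoglobin comparison is claimed. This should be fixed: it is a pediatric dosing ambiguity that points toward the higher dose, and the protocol already contains the rule needed to resolve it.

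**What to change.** State that ages 4 to <12 receive 6 mg/kg/day, maximum 130 mg/day, in either formulation. Allow 65 mg twice-daily tablets in this age group only at a Day 0 weight of at least 21.7 kg (22 kg in practice, where 130 mg/day is 5.9 mg/kg/day), and give lighter children elixir. Make the wording agree in the synopsis and in Sections 3.1, 4.3, 5.2, 6.3.1 and 6.3.5, with a conforming edit to SAP Section 1.3.1.

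This applies the Section 3.2 dose to tablets. One tablet a day for lighter children would keep the tablet option and, at 14 to 20 kg, stay within 3 to 6 mg/kg/day, but it would fall below the selected 6.

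The cost is a protocol clarification in six places. No new data are needed, because Section 6.3.1 already takes weight before dispensing on Day 0. Children at or above 22 kg see no change. The drawback is that some children under that weight who prefer tablets must take a liquid.

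Optionally, SAP Section 7.1 could also report oral dose in mg/kg/day; this can already be derived from the exposure and baseline listings.
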